#### 11.2 Table 3: Mechanistic laboratory assessments

Optional: To be collected only in patients undergoing liver function test monitoring at the Transplant Centre.
 Protocol liver biopsies will be performed at the screening visit and also at 12 and 24 months post successful IS weaning or at 48 months post randomization for patients on maintenance IS treatment.

M months from randomisation

M0 randomisation visit

R To be collected in patients undergoing a for-cause biopsy for suspicion of rejection.

# 12. EFFICACY ASSESSMENT

#### 12.1 Definition of efficacy outcome measures

- Allograft dysfunction: any unexplainable elevation in ALT and GGT relative to baseline and above the upper limit of normality.
- Allograft rejection: will be defined on liver biopsy according to Banff criteria. In rare cases in which it may be not feasible or safe to await the performance of a liver biopsy, episodes of severe allograft dysfunction impairment occurring during weaning that cannot be attributed to any other etiology and that rapidly respond to the empirical re-initiation of immunosuppressive drug therapy will be considered as indicative of presumed allograft rejection.
- *Histopathology of acute allograft rejection:* Acute rejection will be defined by a liver biopsy exhibiting one of the following:

a) Presence of at least 2 of the following 3 features features according to Banff criteria:
 1) predominantly mononuclear portal tract inflammation containing lymphocytes, neutrophils and eosinophils; 2) inflammatory bile duct damage; 3) venous subendothelial inflammation of portal or central veins.

b) Portal and/or lobular inflammation without bile duct damage and subendothelial inflammation provided that: 1) the inflammatory lesions were not present in the baseline (pre-weaning) biopsy; 2) they cannot be attributed to any other etiology (drug toxicity, autoimmunity, viral hepatitis); and 3) they occur in the presence of allograft dysfunction that rapidly normalizes by the re-initiation of immunosuppressive drug therapy. This takes into consideration the fact that in long-term surviving liver transplant recipients acute rejection tends to exhibit less subendothelial inflammation and greater interface and lobular activity resembling chronic hepatitis).

- *Failure of IS withdrawal*: failure to complete IS withdrawal for any reason.
- Operational tolerance: successful withdrawal of IS and maintainance of normal allograft status, as assessed by the absence of allograft dysfunction 12 months after complete IS discontinuation, and by the lack of clinically-significant changes in the liver biopsy obtained 12 months after withdrawal as described in Table 4.

Compartment	Findings				
Portal inflammation and interface	Increased portal inflammation (in comparison with a pre-weaning biopsy				
activity	sample), especially in association with histopathological evidence of				
	tissue damage manifest as: focally worsening or more prevalent				
	lymphocytic bile duct damage, interface hepatitis, fibrosis, or the				
	appearance of definite venous endotheliitis.				
Centrizonal/perivenular	New onset perivenular inflammation (in comparison with a pre-weaning				
inflammation	biopsy sample) associated with even mild perivenular necro-inflammatory				
	activity. Note: these changes might be present in the absence of typical				
	portal changes of rejection.				

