#### 9.2 Secondary endpoints

#### 9.2.1 The secondary clinical endpoints of the trial are defined as:

- Rejection (incidence, severity, timing, steroid resistant rejection, chronic rejection).
- Reasons for failure of IS withdrawal.
- Requirement for IS re-institution despite successful IS withdrawal on the basis of the histological criteria described in Table 5.
- Progression of graft fibrosis in tolerant participants and those on maintenance IS.
- Graft loss.
- All–cause mortality.
- Proportion of tolerant participants remaining free of rejection at 3 years post IS withdrawal.
- Renal function at 1, 2 and 3 years after enrollment.
- Change in co-morbidities associated with IS use (hypertension, cardiovascular risk profile, diabetes mellitus, hyperlipidemia, malignancy).
- Stability of the biomarker signature between baseline and last study visit.
- HrQOL changes associated with IS withdrawal.
- Pharmacoeconomic impact of IS withdrawal.
- Fibroscan:

1- To assess if drug withdrawal results in sequential changes in liver stiffness over time in patients considered tolerant.

2- To evaluate if development of an episode of rejection in patients who do not successfully discontinue immunosuppression increases liver stiffness measurements.

3- To compare changes in liver stiffness over time in patients who remain on maintenance immunosuppression and those who undergo drug weaning.

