- Health Economic Modelling: a health-economic decision-analytic model will be developed with the trial's data to investigate the long-term effects of the two IS withdrawal strategies. We will apply 2 different time horizons: (a) 5 years, and (b) a lifetime horizon, starting with the date of initial IS withdrawal. In line with the NICE reference case all costs and benefits will be discounted by 3.5% for the base case analysis, and the effects of varying discount rates will be investigated using appropriate sensitivity analyses. The 2 different perspectives described above will be analyzed.
- Cost-Utility Analyses: we will evaluate QALYs, costs and the incidence of downstream events including rejection episodes. We will calculate incremental cost-utility ratios (ICERs)

based on differences in patient outcomes and costs. The cost-utility analyses will be conducted using: (a) the trial data and the patient follow-up time frame; and (ii) a 10 year and lifetime horizon. To investigate uncertainty related to the model results we will employ deterministic sensitivity analyses to uncertainty connected to the data inputs, and probabilistic Monte-Carlo-Simulation to assess uncertainty connected to variability. Participants in study arm B+ (IS withdrawal, biomarker-positive) are expected to use lower amounts of drugs than participants in arm B- (biomarker-negative), and to undergo fewer rejection episodes than participants in arm A. The health economic model will allow us to determine if these reduced costs outweigh the costs of biomarker stratification.

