# 16.2 Secondary Analysis

For the exploratory analysis of secondary outcomes, we will use GLMM to adjust stated outcome(s) for study site as a random effect. Multivariate models will include, as fixed effects, the main effects of treatment strategy arm and biomarker status, as well as the interaction term. Secondary analyses are considered exploratory and will not be adjusted for multiple comparisons. A survival analysis approach will additionally be adopted to examine times to acute rejection in patients assigned to IS weaning. For the analysis of serial measures we will use mixed effects regression with random

effects for study subject, as well as for study centre. The stability of the biomarker signature at the final study visist will be tested with GLMM: logistic regression for a binary classification signature and linear regression for a continuous diagnostic score before classification cut-off. The model will include, as fixed effects, the baseline classification or, correspondingly, the baseline estimated probability of tolerance, the main effect of treatment strategy arm and their interaction, as well as study centre, as a random effect. The effect of co-variates (same as for the analysis of the primary outcome and additionally baseline drugs and duration of weaning) will be examined as part of sensitivity analysis. The effect of potential mechanistic mediators on primary and secondary outcomes will be evaluated using generalized latent mixed models (31). This will allow us to consider different models of causation (32). Missing baseline data required for covariate adjustment should not represent an issue for the primary analysis. Patters of missingness of post-randomisation assessments will be examined in relation to the co-variates used for adjustment. If there are two or more outcome time points, missing post-randomisation assessments will be dealt with by fitting GLMMs to all the available data using maximum likelihood methods. If post-treatment variables are found to be predictive of drop-out, multiple imputation will be considered. (R statistics software will be used for statistical analyses (http://www.R-project.org).

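### Two of the rejection routes in Section 12.1 depend on weaning or on restarting immunosuppression, so secondary rejection comparisons that include Arm B- use unequal definitions

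*Protocol*

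**What the plan says.** Section 12.1 gives three ways for an episode to be classed as acute or presumed rejection.

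- **Criterion (a), on biopsy:** "Presence of at least 2 of the following 3 features features according to Banff criteria". It mentions neither weaning nor response to treatment.
- **Criterion (b), on biopsy:** portal and/or lobular inflammation without duct damage or subendothelial inflammation, with no other cause, where "the inflammatory lesions were not present in the baseline (pre-weaning) biopsy" and "they occur in the presence of allograft dysfunction that rapidly normalizes by the re-initiation of immunosuppressive drug therapy". The stated reason is that acute rejection in long-term survivors often takes this form.
- **Presumed rejection, without biopsy:** "episodes of severe allograft dysfunction impairment occurring during weaning that cannot be attributed to any other etiology" and that respond rapidly to restarting IS. The protocol calls these cases rare.

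Chronic rejection by Banff criteria also counts, in any arm.

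Under Section 8.4, Arm B- has no IS reduction for 12 months except for toxicity, and is then managed by each centre's standard of care. Section 5.4 says B- contributes to the secondary clinical outcomes. Section 9.2.1 lists among these "Rejection (incidence, severity, timing, steroid resistant rejection, chronic rejection" and "Proportion of tolerant participants remaining free of rejection at 3 years post IS withdrawal". The multivariate secondary models in Section 16.2 contain "the main effects of treatment strategy arm and biomarker status, as well as the interaction term". Section 12.2 adds, for the cost-utility work, "we will evaluate QALYs, costs and the incidence of downstream events including rejection episodes".

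**The concern.** Presumed rejection needs a weaning period, which B- does not have. Criterion (b) needs IS to be restarted, which cannot happen in someone whose IS was never reduced or stopped. Section 12.1 has no parallel wording for a participant who rejects while on IS and recovers when treatment is intensified. Yet the reason given for criterion (b) applies to every arm: all participants are at least three years post-transplant under Section 6.1.

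Where B- enters a rejection comparison, the same clinical episode could therefore count in Arm A and not in B-. The error runs one way, towards fewer rejections under the biomarker strategy. It touches the benefit that Section 5.4 claims (sparing non-tolerant patients avoidable rejection) and any arm-level reading of the rejection half of the primary objective in Section 5.2.

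A second gap does not involve B-. Section 8.3 foresees rejection after weaning is complete, but presumed rejection is confined to the weaning period. A late episode too urgent for biopsy has no route into the 3-year rejection-free endpoint.

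**Working it through.** **1. Who can meet each route**

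| Route | A and B+ | B-, IS unchanged | B-, IS reduced then restored |
|---|---|---|---|
| Criterion (a) | yes | yes | yes |
| Banff chronic rejection | yes | yes | yes |
| Criterion (b) | yes | no | possible |
| Presumed rejection | during weaning only | no | no |

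The pre-weaning biopsy named in criterion (b) is not an obstacle: every participant has a screening biopsy (Section 10.8). The response condition is what excludes B-.

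**2. Which analyses include B-**

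- Primary analysis (Sections 9.1, 15, 16.1): A versus B+ only. Both groups are weaned and all routes apply alike, so this asymmetry causes no bias.
- Time to acute rejection (Section 16.2): participants assigned to weaning only, so again no bias.
- Exploratory models with arm, biomarker status and interaction (Section 16.2): B- is included, so these are exposed.
- Rejection event counts compared by strategy (Section 12.2): exposed if B- is counted.

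**3. The protocol's sample size is untouched**

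Inputs from Section 15: success 50% in A and 80% in B+, 2:1 allocation, 90% power, 5% type I error (taken as two-sided). With unpooled variance:

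n(A) = (1.960 + 1.282)² × (0.25 + 0.16/0.5) / 0.30² = 66.5, and n(B+) = 33.3; total 99.8, i.e. 100.

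With an equal-sized B- group the total is 67 + 67 = 134, and 134 × 1.10 = 147.4, i.e. 148. These are the stated figures, and none depends on how rejection is classified in B-.

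**4. Size of the shift where B- is included**

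Let r be the true B- rejection rate and f the share of those episodes that only criterion (b) or presumed rejection would catch. The protocol gives neither, so both are assumptions. Half of Arm B is expected to be biomarker-negative (Section 15), about 37 of 74.

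- Understatement of Arm B incidence = 0.5 × r × f
- Understatement of B- incidence (A-negative versus B-) = r × f
- B- episodes not counted = 37 × r × f

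For scale, treat every weaning failure as a rejection: 50% in A and 20% in B+. The true A versus B difference is then 50% − (0.5 × 20% + 0.5 × r).

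| r | f | Arm-level shift (points) | Biomarker-negative shift (points) | Episodes missed of 37 | True A v B difference (points) |
|---|---|---|---|---|---|
| 2% | 10% | 0.1 | 0.2 | 0.07 | 39 |
| 2% | 50% | 0.5 | 1.0 | 0.37 | 39 |
| 5% | 50% | 1.25 | 2.5 | 0.93 | 37.5 |
| 10% | 10% | 0.5 | 1.0 | 0.37 | 35 |
| 10% | 50% | 2.5 | 5.0 | 1.85 | 35 |
| 15% | 75% | 5.6 | 11.3 | 4.2 | 32.5 |

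At r = 10% and f = 50%, for example, Arm B would show 12.5% instead of 15.0%.

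Treating all failures as rejections makes the difference as large as it can be. If only half were rejections (25% in A, 10% in B+), the true difference at r = 10% would be 25 − (5 + 5) = 15 points, with the same 2.5-point shift.

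**5. The 3-year endpoint**

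This concerns tolerant participants, so B- plays no part and A and B+ are treated alike. Biopsied late rejections still count by (a), (b) or Banff chronic rejection. Only unbiopsied late episodes are lost, and the protocol gives no number for them.

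**The case against.** The strongest reply is that nothing confirmatory is affected. The powered hypothesis, the primary analysis and the time-to-rejection analysis all leave B- out, and Section 16.2 labels the secondary analyses exploratory. That stands. A reader might infer that the trial's rejection comparison as a whole is tilted towards the biomarker strategy; the documents support this only for contrasts that include B-.

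A reader might also infer that B- can meet only classical Banff acute rejection. That is too absolute. Banff chronic rejection stays open. Section 8.4 allows reduction for toxicity and, after month 12, management by standard of care, so some B- participants could have IS reduced and restored and so meet criterion (b).

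Presumed rejection is described as rare and should not be weighed as a main route. The cost-utility effect is narrow too: resource use comes from its own questionnaire and EQ-5D is collected on a schedule, whatever label an episode receives. Only the event count moves.

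Large magnitudes need both assumed rates at the high end. B- participants are stable recipients without rejection in the previous 52 weeks who remain on IS, so low rates are plausible.

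Finally, widening the definition has a price. B- participants know their biomarker status (Section 5.4), and a response to intensified treatment is a less specific criterion than histology. This is a fair objection and shapes the fix.

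The rule itself survives these points: applied as written, it counts like episodes differently by arm, and always in the same direction.

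**Conclusion.** The point holds as a minor defect of endpoint definition. Followed exactly, Section 12.1 under-counts rejection in B- participants who remain on IS, and so in the biomarker strategy, wherever B- is part of a rejection-incidence comparison. It does not touch A versus B+, time to rejection, or the sample size of 148.

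The protocol does not allow the size to be derived. The arm-level shift is 0.5 × r × f: about 0.1-2.5 points for r of 2-10% and f of 10-50%, and up to 5.6 points at r = 15% and f = 75%. In the biomarker-negative contrast the figures double. Against the 32.5-39 point arm-level difference implied by the planning figures this is small, and it would be unlikely to change a conclusion. That comparison rests on reading all weaning failures as rejections.

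The loss of late presumed rejections from the 3-year endpoint is a separate gap, equal in A and B+ and not quantifiable from the protocol. It is not evidence of bias between arms.

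**What to change.** Amend Section 12.1 for endpoint classification only, with no change to how any episode is treated:

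1. In criterion (b) and in presumed rejection, let the response condition read *re-initiation of, or increase in or addition to, immunosuppressive therapy as given by the treating centre*.
2. Let presumed rejection occur *at any time after randomisation* instead of only during weaning.
3. Report every rejection comparison that includes B- a second time, as a sensitivity analysis, using only the biopsy criteria common to all arms: criterion (a) and Banff chronic rejection.

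The cost is one or two sentences, the matching rejection item on the case report form, and one extra analysis. No visits or procedures are added. The downside is that a few more, less specific rejections may be counted in B-, where participants know their biomarker status, and in late follow-up. The common-criterion analysis shows how much this matters.

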# Table 4. Banff Liver Allograft Pathology Working Group Criteria of Operational Tolerance Failure in Patients Off Immunosuppression

# Table 4. Banff Liver Allograft Pathology Working Group Criteria of Operational Tolerance Failure in Patients Off Immunosuppression

Compartment	Findings
Bile duct changes	New-onset biliary epithelial cell senescence changes or ductopenia when
	sampling problems and/or an alternative, non-immunological explanation
	(e.g. biliary strictures) can be reasonably excluded
Fibrosis**	Greater than 1 grade increase in fibrosis in any one compartment: (a)
	portal/periportal; (b) peri-sinusoidal; or (c) perivenular fibrosis; or new
	onset bridging fibrosis without an alternative explanation (e.g. biliary
	strictures) that is reasonably prevalent and not readily explained by a
	possible sampling error.
Arteries	Any evidence of foam cell or obliterative arteriopathy

\*Patients with underlying AIH, HCV, PBC, or PSC are excluded (25).
\*\* Fibrosis should be graded as follows (26):Portal/periportal: 0 – 3
Peri-sinusoidal: 0 – 3.
Perivenular: 0 – 3.

#### Table 5. Follow-Up Biopsy Findings in Patients Off IS that Should Prompt Re-Institution of IS

Compartment	Findings
Portal inflammation and interface activity	Development of moderate portal inflammation or moderate interface activity in most portal tracts.
Centrizonal/perivenular inflammation	Central perivenulitis in most central veins.
Bile duct changes	New-onset biliary epithelial cell senescence changes or ductopenia when sampling problems and/or an alternative, non-immunological explanation (e.g. biliary strictures) can be reasonably excluded
Fibrosis	At least a 2 grade increase in fibrosis in any one compartment (according to Venturi et al (26)).
Arteries	Any evidence of foam cell or obliterative arteriopathy

#### 12.2 Pharmaco-economic and quality of life assessments

Health related Quality of Life (HrQOL) Assessment: we will employ the Short-Form 36 Health Survey (SF-36) and/or the EQ-5D as generic surveys. SF-36 represents the most prominent generic measure in assessing patient's HrQOL following liver transplantation (27). In contrast, EQ-5D is the preferred generic measure for assessing QOL in adults, according to the Reference Case by NICE (28). By applying preference values from population studies to EQ-5D health states we will be able to generate utility values that will be used in quality-adjusted life years (QALY) and cost-per-QALY-analyses (28, 29). In addition, we will also assess QOL using disease-specific questionnaires (29, 30). The NIDDK Liver Transplant Database QOL questionnaire contains 63 items on 6 subscales that cover general health, role function, social function, psychological status, personal function, and measures of liver disease (27). Participants will be asked to complete the stated questionnaires on the following time points: inclusion, months 3, 6, 9, 12, 18, 24, 36, 48 (final study visit), and in case of rejection episodes. We expect differences in QOL to occur between arm A and B and between arm B+ and B-. Due to the higher risk of rejection, during the initial 6-9 months of the study QOL of B+ participants could be worse than those in arm B-. In the long run, they might be better off due to the fact that they are not dependent on IS and may have a reduction in IS side effects.

Assessment of Costs: costs will be assessed both from a healthcare and a societal perspective. For the healthcare perspective, only direct costs that accrue during the study period will be assessed (i.e. costs for IS medication, clinical visits, admissions, biomarker stratification). For the societal perspective, additional costs such as patient's absence from work, among others, will be accounted for. Resource utilization will be measured during the trial using a specific questionnaire, that will capture drug utilization, hospitalization, and diagnostic, therapeutic, and laboratory services consumed by patients. Resource utilization will be valued using prices relevant to the NHS. To calculate expected costs for the biomarker-guided weaning strategy, a micro-costing of the stratification process will be conducted.

- Health Economic Modelling: a health-economic decision-analytic model will be developed with the trial's data to investigate the long-term effects of the two IS withdrawal strategies. We will apply 2 different time horizons: (a) 5 years, and (b) a lifetime horizon, starting with the date of initial IS withdrawal. In line with the NICE reference case all costs and benefits will be discounted by 3.5% for the base case analysis, and the effects of varying discount rates will be investigated using appropriate sensitivity analyses. The 2 different perspectives described above will be analyzed.
- Cost-Utility Analyses: we will evaluate QALYs, costs and the incidence of downstream events including rejection episodes. We will calculate incremental cost-utility ratios (ICERs)

based on differences in patient outcomes and costs. The cost-utility analyses will be conducted using: (a) the trial data and the patient follow-up time frame; and (ii) a 10 year and lifetime horizon. To investigate uncertainty related to the model results we will employ deterministic sensitivity analyses to uncertainty connected to the data inputs, and probabilistic Monte-Carlo-Simulation to assess uncertainty connected to variability. Participants in study arm B+ (IS withdrawal, biomarker-positive) are expected to use lower amounts of drugs than participants in arm B- (biomarker-negative), and to undergo fewer rejection episodes than participants in arm A. The health economic model will allow us to determine if these reduced costs outweigh the costs of biomarker stratification.

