#### 4.3 Scientific Rationale

Long-term survival after solid organ transplantation has increased during the last decades (23) due to improvements in surgical technique, peri-operative care, and more efficient IS. However, transplant recipients still exhibit higher morbidity and mortality than the general population. One of the main causes are co-morbidities negatively influenced by chronic IS drug usage (24). Minimization (or complete withdrawal) of IS, particular CNIs, may overcome these problems and has become a priority goal in transplantation. The clinical opportunity is more tangible in the liver than in other transplantation settings due to the greater capacity of the liver allograft to cope with the cytolytic effects of alloimmune responses. The potential benefits of IS minimization or withdrawal, however, still need to be balanced with the risks and inconveniences of prompting liver allograft rejection. The recent observation that operational tolerance can be predicted employing a combination of clinical parameters and molecular biomarkers would modify the equipoise in favour of discontinuing IS in previously identified operationally tolerant recipients. Identification of a reproducible and reliable tolerance signature would therefore substantially benefit the liver transplant population. In Europe approximately 6000 liver transplants are performed every year (700 of them in the UK). Under the current standard-of-care indefinite pharmacological IS is prescribed to all of them. The cost of immunosuppressive drugs is £3000- £5000/patient/year. In addition to its cost, chronic IS results in substantial side effects (hypertension, diabetes, renal failure, hyperlipidaemia, cancer, infections) that contribute to patient morbidity and mortality. The implementation of tolerance biomarkers would reduce the cost of medical management in liver transplantation, reduce the negative impact of co-morbidities associated with the use of chronic IS, and increase the quality of life of liver recipients.

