### 5.3 Secondary Objectives:

- 1) To establish the safety of biomarker-guided IS withdrawal.
- 2) To determine the health-economic impact of withdrawing IS in liver transplant recipients and to assess how much this cost is influenced by the use of a diagnostic test of operational tolerance.
- 3) To assess the effect of IS withdrawal on the quality of life of liver transplant recipients.
- 4) To determine the extent to which IS withdrawal improve drug-related co-morbidities.
- 5) To investigate if liver transplant recipients under IS become operationally tolerant over time.
- 6) To determine if the presence of donor-specific anti-HLA antibodies influence the success of IS withdrawal, and whether IS withdrawal promotes the development of anti-HLA antibodies in liver transplant recipients.
- 7) To explore the association between operational liver transplant tolerance, iron metabolism, immunosenescence, and specific gut microbiome profiles.

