### 5.4 Trial Design

This is a prospective, multi-centre, phase IV, biomarker-strategy design trial with a randomised control group in which adult liver transplant recipients will undergo IS withdrawal. Enrolled participants will be randomised 1:1 to either: 1) Non-Biomarker-based IS weaning (Weaning-All; Arm A); or 2) Biomarker-based IS weaning (Arm B). In participants allocated to Arm A IS will be withdrawn regardless of the result of the biomarker test. Among participants allocated to Arm B, only those found to be biomarker-positive (Arm B+, i.e. potentially tolerant) will be offered IS withdrawal, while biomarker-negative participants (Arm B-, i.e. potentially non-tolerant) will remain on their

baseline maintenance IS. This will allow us to demonstrate that the biomarker is a useful test to personalise IS by offering drug withdrawal only to those participants who are likely to complete the process successfully, avoiding unnecessary rejections among those who have not developed tolerance. Comparing the outcome of IS withdrawal between arms A and B+ will provide direct evidence of the clinical usefulness of the test as a function of its predictive accuracy. We have established that for the biomarker to drive safe IS withdrawal its Positive Predictive Value  $(PPV = \frac{Number Actually Tolerant}{Number Biomarker+})$  should be no less than 0.80, and its sensitivity at least 070. To account for centre effects, we will use stratified randomization. Furthermore, to avoid biases, participants undergoing drug withdrawal and their physicians will be blinded to the biomarker results. Participants randomized to Arm B- will know their biomarker status, and will be maintained in the study until they complete 48 months of follow-up post randomisation. They will contribute to secondary clinical outcomes and to the evaluation of the stability of the tolerance signature.

Cost and quality of life (HrQOL) assessments will be conducted alongside the trial to estimate the health-economic implications of the 2 different strategies. Furthermore, sequential biological specimens will be collected to conduct ancillary mechanistic studies. Recruitment will take place in 14 European liver transplant units (King's College Hospital, Royal Free London, Newcastle, Birmingham, Leeds, Edinburgh, Cambridge, Leuven, Hannover, Berlin, Barcelona, Dublin, Cliniques Universitaires Saint-Luc and Palermo-ISMETT).

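### The economic model compares the two withdrawal strategies only, so the first half of objective 2 and the saving claimed against lifelong immunosuppression have no planned estimate

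*Protocol*

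**What the plan says.** Secondary objective 2 (section 5.3) has two parts. The first is "To determine the health-economic impact of withdrawing IS in liver transplant recipients". The second is to assess how far a diagnostic test of tolerance influences that cost.

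Section 5.4 says the cost and quality-of-life work will estimate the "health-economic implications of the 2 different strategies". Section 12.2 specifies the decision-analytic model "to investigate the long-term effects of the two IS withdrawal strategies", with horizons that start at the date of first IS withdrawal. Neither section names a strategy in which everyone stays on IS.

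The rationale in section 4.3 takes a different reference point. It says of liver recipients: "Under the current standard-of-care indefinite pharmacological IS is prescribed to all of them". It puts drug cost at £3000-£5000 per patient-year and concludes: "The implementation of tolerance biomarkers would reduce the cost of medical management in liver transplantation".

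Maintenance IS enters the cost argument of section 12.2 only through Arm B-. That section expects B+ to consume less medication than B- and to have fewer rejections than Arm A. The paragraph then ends: "The health economic model will allow us to determine if these reduced costs outweigh the costs of biomarker stratification".

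**The concern.** The impact of withdrawing IS can only be measured against not withdrawing it. The saving in section 4.3 is likewise a saving against current practice, where everybody stays on drugs. Both strategies in the model are withdrawal strategies, so neither quantity is estimated.

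The closing argument of section 12.2 does not fill the gap. It takes lower drug use from B+ against B- and fewer rejections from B+ against A, then sets both against the cost of testing. These are contrasts between subgroups with different reference groups, not comparisons of whole strategies. B+ and B- differ by biomarker status by definition, so their difference in drug use mixes the effect of withdrawal with the patient characteristics that the test picks out.

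A payer considering a move from lifelong IS to test-guided withdrawal would therefore receive an estimate against Weaning-All, which by section 4.3 is not current practice.

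**Working it through.** **Inputs**

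- Section 15: 50% biomarker-positive; 50% successfully weaned in Arm A; 80% in Arm B+ under the alternative; required sensitivity at least 0.70.
- Section 4.3: IS for all under current care; drug cost c = £3000 to £5000 per patient-year.
- Section 4.1.1: re-calibrated test, sensitivity 72%; the earlier European adult trial weaned 42 of 102.
- Section 12.2: discount rate 3.5%.
- Assumption, not in the protocol: a patient who fails weaning returns to IS at baseline cost.

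**The plan's own figure.** The protocol gives no drug cost by strategy, but its sample size rests on the same rates and reproduces. With unpooled variance, two-sided 5%, 90% power and 2:1 allocation, n in Arm A = (1.960 + 1.282)² × (0.25 + 0.16/0.5) / 0.30² = 66.5. The total is 66.5 × 1.5 = 99.8, so 100. Adding B- gives about 134, and 134 × 1.10 = 147.4, so 148.

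**Share off IS**

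- Arm A: 0.50
- Arm B: 0.50 × 0.80 = 0.40 (implied sensitivity 0.40/0.50 = 0.80)
- Continued IS for all: 0

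**Maintenance drug cost per patient-year = c × (1 − share off IS)**

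| Strategy | c = £3000 | c = £5000 |
|---|---|---|
| Weaning-All (A) | 1500 | 2500 |
| Biomarker-guided (B) | 1800 | 3000 |
| Continued IS for all | 3000 | 5000 |
| B minus A | +300 | +500 |
| B minus continued IS | −1200 | −2000 |
| A minus continued IS | −1500 | −2500 |

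Over five years at steady state, with payments at the start of each year, the discount factor is the sum of 1/1.035^t for t = 0 to 4, which is 4.673. B minus A is about +£1400 to +£2340. B minus continued IS is about −£5610 to −£9350.

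**Other test performance**

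| Tolerant share | Sensitivity | Off IS in B | B minus A | B minus continued IS |
|---|---|---|---|---|
| 0.50 | 0.70 | 0.35 | +450 to +750 | −1050 to −1750 |
| 0.50 | 0.72 | 0.36 | +420 to +700 | −1080 to −1800 |
| 42/102 = 0.41 | 0.72 | 0.30 | +346 to +576 | −889 to −1482 |

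Under the stated assumption the direction does not depend on the rates. The share off IS in B is sensitivity × tolerant share, which cannot exceed the tolerant share reached in A. The gap closes only at sensitivity 1.

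**How much the assumption matters.** Failed weans are 0.50 of Arm A and 0.50 × 0.20 = 0.10 of Arm B, a difference of 0.40. Extra drug spending per failed wean that would cancel the B minus A gap is 300/0.40 = £750 to 500/0.40 = £1250 per year, or about £3500 to £5840 over five years discounted. The protocol gives no figure for this spending.

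**The case against.** Five points can be made for the plan.

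- **A against B is a proper question.** It is the right comparison for the second half of objective 2, and a whole-strategy model would net fewer rejections against more maintenance IS and the cost of the test. This stands. A reader might infer that the model cannot answer objective 2 at all; the wording of the objective does not support that.
- **Maintenance IS is not absent.** B- participants have no planned reduction for 12 months apart from management of toxicity, then follow centre practice (section 8.4), and are followed for 48 months. Section 12.2 compares them with B+. This stands as a source of data, but B- is a biomarker-negative subgroup and does not represent a strategy for all recipients.
- **The restriction is written for the model.** The cost-utility paragraph names no pair of strategies for its incremental ratios, and further detail may sit in a later analysis plan. That is fair, but sections 5.4 and 12.2 both state the scope as two strategies, and an analyst following them would stop there.
- **The figures cover drugs only.** Section 12.2 also costs visits, admissions and stratification, and section 8.6 allows added treatment after rejection. This stands, and it limits what the figures show.
- **Leaving out a maintenance comparison was deliberate.** Section 15 explains that superiority over maintenance IS on hard clinical outcomes would need an unrealistic sample size and follow-up. That explains why there is no randomised maintenance arm. It does not prevent a modelled one.

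**Conclusion.** The point holds as a gap in the comparators. As written, section 12.2 yields no valid estimate for the first half of objective 2, or for the saving in section 4.3. At plan rates, maintenance drug cost under biomarker guidance is £300-£500 per patient-year above Weaning-All and £1200-£2000 below continued IS for all, so the choice of reference strategy decides the sign of the drug-cost increment.

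This rests on the section 15 rates, the section 4.3 cost range and failed weans returning to baseline-cost IS. A reader might go further and infer that the planned analysis would wrongly show the test to be costly. The protocol does not support that. The two contrasts answer different questions and may properly differ in sign. Net cost cannot be derived because unit costs for rejection, biopsy, admission and the test are not given. Extra drug spending of about £750-£1250 per failed wean per year would remove the gap with Weaning-All. The matter concerns a secondary objective and leaves the primary analysis untouched.

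**What to change.** In section 12.2:

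1. Add continued IS for all as a third modelled strategy and report a full incremental analysis of the three.
2. Measure model time from randomisation, because the date of first withdrawal does not exist for patients who are never weaned.
3. For biomarker-negative patients on maintenance, use Arm B- data. For biomarker-positive patients on maintenance, use their recorded baseline IS regimens with B- event rates, and vary both in the deterministic and probabilistic sensitivity analyses already planned.
4. Tie each comparison to its purpose: A against B for the influence of the test, and each withdrawal strategy against continued IS for the impact of withdrawal. Drop the argument that combines B+ against B- with B+ against A.

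The cost is modelling work. Medication is recorded at baseline, and the economic and EQ-5D questionnaires are already scheduled every six months, so no extra patients or visits are needed. The downside is that maintenance outcomes in biomarker-positive patients rest on an assumption, because none are randomised to maintenance. B- regimens may also change under centre practice after month 12, which the sensitivity analyses should cover.
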